9.3.2 ADA summaries

The following outputs will be presented on the SS.

Tables:

- Number and percentage of study participants with positive, negative, inconclusive or missing ADA sample status at the time of each visit will be summarized by treatment group and RLZ total. Denominator is the number of study participants having a non-missing result at that visit. The same table will be repeated for NAb sample status (positive, negative, missing).
- Number and percentage of study participants in each of the individual and combined ADA participant status categories presented in **Error! Reference source not found.** will be summarized by treatment group and RLZ total.
- Total prevalence of pre-existing ADA and NAb, defined as number and percentage of participants having an ADA positive sample status at baseline, with the denominator being the total number of study participants having an evaluable sample result at Baseline. Missing samples will not be included in the denominator. The same will be repeated for NAb.
- The first occurrence of treatment-emergent ADA positivity: cumulative number and percentage of TE-ADA positive participants (category 7) who are ADA positive for the first time at each visit.
- Summary table of mean maximum percentage CFB in total IgG and mean CFB in MG-ADL total score at Day 43, summarized by ADA participant categories 1, 2, 9, 10, 11 and 12 for the corresponding time period of interest (up to Day 43) and by treatment group and RLZ total.

- Overall summary table of TEAEs within each of the ADA participant categories 1, 2, 7 and 8.
- Summary table of incidence of TEAEs by ADA participant category 1, 2, 7 and 8.
- Summary table of AEOF hypersensitivity reactions, anaphylactic reactions and infusion reactions by ADA participant category 1, 2, 7 and 8.

Figures:

- Individual time course plots for study participants with at least one ADA positive sample, representing ADA and NAb titers (on log-scale), rozanolixizumab plasma concentrations, percentage CFB for total IgG and MG-specific autoantibodies, and CFB for MG-ADL total score. The sub-title of the graph will include the study participant number, bodyweight category, treatment group, ADA participant category (2, 3,4,5,6). The dosing will be represented in the x axis with bars/arrows at the time of dose.
- Spaghetti plots of individual time course of ADA titer for ADA positive participants in categories 9, 10, 11 and 12, whereby all categories are overlaid on the same plot and visualized using different symbols and colors. The ADA titer results will be presented on a log-scale. Dosing time points should be indicated below the x-axis. The same plot will be repeated for NAb titer for NAb positive participants in categories 9 and 11.
- A box-and-whisker plot of maximum post-dose ADA titer (on log-scale) through the end of the observation period versus ADA participant category for categories 9, 10, 11 and 12. The same plot will be repeated for NAb titer for ADA participant categories 9 and 11.
- Scatter dot plot of individual rozanolixizumab post-dose plasma concentrations categorized by Day (i.e. Days 3, 6, 24, 38, 41) and for each Day by ADA participant categories 1, 2, 9, 10, 11 and 12. Individual samples that tested positive for ADA will be visualized using a symbol and/or color.
- Time course plot of mean change from Baseline in MG-ADL total, summarized by ADA participant category 1, 2, 7, and 8. Categories will be determined for the time period from baseline up to Day 43. Separate plots for each treatment group and RLZ total. The sample plot will be repeated for NAb related categories 9, 10, 11, 12.
- Spaghetti plots of individual time course of percentage CFB for total IgG, for each of the ADA participant categories 1, 2, 9, 10, 11 and 12, whereby the ADA participant categories are multipaneled. Separate plots for each treatment group and RLZ total ([REDACTED] combined). Individual samples that tested positive for ADA will be visualized using a symbol and/or color. Dosing time points should be indicated below the x-axis.
- Scatter dot plot of individual CFB in MG-ADL total score categorized by ADA titer tertile (including category ADA not present) over time. The same plot will be repeated for NAb titer.
- Scatter dot plot of individual percentage CFB for total IgG categorized by ADA titer tertile (including category ADA not present) over time. The same plot will be repeated for NAb titer.

Listings:

- By-subject listing by treatment group, individual ADA participant category, screening and confirmatory assay results, ADA titer, fold change compared to baseline, and whether or not sample contains RLZ concentration above drug tolerance. In addition, the time since administration of IMP will be reported (in days).
- By-subject listing by treatment group, administered RLZ dose and timepoint, of ADA and NAb sample status, ADA titer, NAb titer, rozanolixizumab plasma concentration, CFB for total IgG, CFB for MG-specific autoantibodies, CFB for MG-ADL total score, QMG and MG-C, and individual ADA participant classifications. In addition, the time since administration of IMP will be reported (in days).
- By-subject listing of abovementioned TEAEs, the time of onset, the ADA and NAb sample status and ADA and NAb titers at the closest sampling time point prior to and subsequent to the TEAE, and time since last administration of IMP (in days).

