1.3 Schedule of Activities

Procedure	Screening	Treatment Period									Observation Period			
		V1	V2 (BL)	V3 ^a	V4	V5	V6	V7 ^a	V8	V9	V10 (EOT or PEOT)	V11 ^b	V12	V13 ^b
Day (days) ^c	-28 to -1	1	3(±1)	8(±2)	15(±2)	22(±2)	24(±1)	29(±2)	36(±2)	43(±2)	57(±3)	71(±4)	85(±3)	99(±4)
Written informed consent	X													
Optional PK sub-study consent ^d	X													
Demographic and Baseline ^e	X	X												
Verification of inclusion/exclusion criteria	X	X												
Prior and concomitant medications and medical procedures	X	X		X	X	X		X	X	X	X	X	X	X
General medical history	X													
Psychiatric history/C-SSRS	X													
Query for suicidality ^f		X		X	X	X		X	X	X		X		X
Chest X-ray ^g	X													
IGRA TB test ^h	X													
TB Signs and Symptoms questionnaire	X	X								X				X
12-lead ECG	X	X		X						X				X
Full physical examination	X	X								X		X		X
Brief physical examination				X	X	X		X	X					
Pregnancy test (serum)	X													
Pregnancy test (urine) ⁱ		X						X						X
Hematology, serum chemistry, urinalysis	X	X		X		X			X	X		X		X

Procedure	Screening	Treatment Period									Observation Period			
Visit	V1	V2 (BL)	V3 ^a	V4	V5	V6	V7 ^a	V8	V9	V10 (EOT or PEOT)	V11 ^b	V12	V13 ^b	V14 (EOS)
Day (days) ^c	-28 to -1	1	3(±1)	8(±2)	15(±2)	22(±2)	24(±1)	29(±2)	36(±2)	43(±2)	57(±3)	71(±4)	85(±3)	99(±4)
PTT and INR measurements	X	X												X
Serology testing for HIV, Hepatitis B, and Hepatitis C	X													
Anti-tetanus toxoid titer		X								X				X
Vital signs	X	X	X	X	X	X	X	X	X	X		X		X
Call or enter IRT to register the visit	X			X	X	X		X	X	X				X
Call or enter IRT/ Randomization		X												
Study participants identification card assigned		X												
Recording of AEs	X	X	X	X	X	X	X	X	X	X	X	X	X	X
Study drug administration ^j		X		X	X	X		X	X					
Blood sampling for PK ^k		X	X		X		X			X				
Blood sampling for ADA	X	X			X		X			X		X		X
Blood sampling for exploratory safety biomarker analysis ^l		X												
Blood sampling for future exploratory biomarker analysis		X		X										X
Blood sampling for total IgG and IgG subclasses	X	X		X	X	X		X	X	X		X		X
Blood sampling for IgA, IgM, IgE		X								X				X
MG-specific autoantibodies ^m		X			X			X		X		X		X
Serum complement levels (C3,C4) and cytokines ⁿ		X							X					

Procedure	Screening	Treatment Period									Observation Period			
Visit	V1	V2 (BL)	V3 ^a	V4	V5	V6	V7 ^a	V8	V9	V10 (EOT or PEOT)	V11 ^b	V12	V13 ^b	V14 (EOS)

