Study participants who are identified as being treatment-induced or treatment-boosted ADA-positive will be grouped as treatment-emergent (TE)-ADA positive participants. Study participants who are identified as being treatment-reduced or treatment-unaffected ADA-positive will be grouped as non-TE-ADA positive participants. Both TE-ADA positive and non-TE-ADA positive participants will be further classified as NAb negative or NAb positive.

The individual and combined ADA participant categories will be summarized through the end of the 8-week observation week (Day 99), unless specified otherwise.

Table 9–1: Terms and Definitions for ADA Evaluation in Study Participants

Classification	Classification Label	Definition
Individual participant categories		
1	Pre-ADA negative – treatment induced ADA negative (ADA-NEG)	Study participants who have an ADA negative sample at Baseline and all sampling points post-Baseline up to the timepoint of interest.
2	Inconclusive	Study participants who have an ADA positive or negative Baseline sample and some post-Baseline samples are missing or inconclusive, while other post-Baseline samples are ADA negative up to the timepoint of interest.
3	Pre-ADA negative – treatment induced ADA positive (TI-POS)	Study participants who have an ADA negative sample at Baseline and have least one ADA positive sample at any sampling point post-Baseline up to the timepoint of interest.
4	Pre-ADA positive – treatment boosted ADA positive (TB-POS)	Study participants who have an ADA positive sample at Baseline and at least one ADA positive sample at any sampling point post-Baseline up to the timepoint of interest, with increased titer values compared to Baseline (greater than a predefined fold difference increase from Baseline value which will be defined within the validation of the assay i.e. MSR of the assay ^a).
5	Pre-ADA positive – treatment reduced ADA positive (TR-POS)	Study participants with an ADA positive sample at Baseline, and ADA negative samples at all sampling points post-Baseline up to the timepoint of interest.
6	Pre-ADA positive – treatment unaffected ADA positive (TU-POS)	Study participants with an ADA positive at Baseline and an ADA positive sample at any sampling point post-Baseline up to timepoint of interest with titer values of the same magnitude as Baseline (less than a predefined fold difference from the Baseline value which will be defined within the validation of the assay, i.e. MSR of the assay ^a).

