Combined participant categories		

7	Treatment emergent ADA positive (TE-POS)	Includes study participants who are treatment induced ADA positive (category 3) or treatment boosted ADA positive (category 4).
8	Non-treatment emergent ADA positive (Non-TE-POS)	Includes study participants who are treatment reduced ADA positive (category 5) or treatment unaffected ADA positive (category 6).
9	Treatment emergent ADA positive – NAb positive (TE-POS, Nab-POS)	Includes study participants who are treatment emergent positive (category 7) and have at least one NAb positive sample
10	Treatment emergent ADA positive – NAb negative (TE-POS, Nab-NEG)	Includes study participants who are treatment emergent positive (category 7) and have no NAb positive samples
11	Non-treatment emergent ADA positive-- NAb positive (Non-TE-POS, NAb-POS)	Includes study participants who are non-treatment emergent positive (category 8) and have at least one NAb positive sample
12	Non-treatment emergent ADA positive-- NAb negative (Non-TE-POS, NAb-NEG)	Includes study participants who are non-treatment emergent positive (category 8) and have no NAb positive samples

^a The fold difference increase from baseline value, i.e. the minimum significant ratio (MSR) determined during assay validation, will be reported in the relevant tables, listings and figures. It reflects the fold difference in titer level that considered higher than the assay variation in titer determination

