- The time to achieving treatment-emergent ADA positive, separated by treatment group and ADA category, will be analyzed based on Kaplan-Meier methods.
- The incidence of NAb, defined as (cumulative) proportion of study participants having NAb positive samples at any point up to and including that time point will be summarized by treatment group and RLZ total. Missing samples will not be included in the denominator. This will be also plotted graphically overlaying the treatment groups.
- A summary table of all immune related TEAEs by ADA status will be presented by treatment group. For this summary, study participants will be presented for TEAEs occurring prior to becoming treatment emergent ADA positive, TEAEs occurring after becoming TE ADA positive, and TEAEs for study participants who remained TE ADA negative.

Safety endpoints

The number, percentage of study participants and frequency of TEAEs will be summarized by treatment group and RLZ total. Additional details are as follows:

- An TEAE overview table will be provided, include following categories: any TEAEs, serious TEAEs, participant discontinuation due to TEAEs, permanent withdrawal of IMP due to TEAEs, temporary withdrawal of IMP due to TEAEs, treatment-related TEAEs, severe TEAEs, TEAEs leading to death, all deaths (AEs leading to death).
- Incidence of TEAE will be summarized by SOC, HLT, and PT for:
 - Any TEAEs
 - Severe TEAEs
 - Any TEAEs by maximum intensity (mild, moderate and severe)
 - Any TEAEs by relationship
 - Fatal TEAEs
 - Serious TEAEs
 - Serious TEAEs by relationship
 - Participant discontinuation due to TEAEs
 - TEAEs leading to permanent withdrawal of IMP

Treatment-emergent AESMs (Headache, Gastrointestinal disturbances and Opportunistic infections)

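### The all-region safety-by-ADA tables fix ADA category through Day 99, so in treatment-induced participants reactions before the first detected positive sample count as reactions under ADA positivity; a split at positivity is planned for Japan only

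*SAP*

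**What the plan says.** SAP 9.3.2 lists three safety outputs by ADA participant category: an overview of TEAEs, TEAE incidence, and a "Summary table of AEOF hypersensitivity reactions, anaphylactic reactions and infusion reactions by ADA participant category 1, 2, 7 and 8". None gives a time window or a rule linking event onset to ADA status. SAP 10.2.3 names the reaction table again, also without such a rule. The default is in SAP 9.3.1: "The individual and combined ADA participant categories will be summarized through the end of the 8-week observation week (Day 99), unless specified otherwise".

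The categories describe the participant, not the event. Category 3 (treatment-induced) covers participants who are ADA negative at Baseline and "have least one ADA positive sample at any sampling point post-Baseline up to the timepoint of interest". Category 7 (treatment-emergent positive) combines category 3 with category 4, the boosted participants, who were already positive at Baseline. Category 8 combines categories 5 and 6, also positive at Baseline.

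Other parts of the SAP handle timing differently:
- For the plot of MG-ADL change by ADA category, 9.3.2 says: "Categories will be determined for the time period from baseline up to Day 43".
- SAP 11.1, for Japan only, tabulates immune-related TEAEs as "TEAEs occurring prior to becoming treatment emergent ADA positive, TEAEs occurring after becoming TE ADA positive", with a third group that stayed negative.
- For all regions, 9.3.2 also plans a listing of these TEAEs with onset, ADA and neutralizing-antibody results at the nearest samples either side, and time since last dose. A separate table gives first treatment-emergent positivity by visit.

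**The concern.** A table of reactions by ADA category invites a simple reading: do participants with antibodies react more often? Under the Day 99 default, a category 3 participant's whole event history goes to category 7, including infusions given while every available sample was negative. Status is fixed by later samples, and an event can be classified by a sample taken weeks after it.

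If antibodies raise the risk of infusion-linked reactions, mixing in infusions from before the antibodies arose moves the tabulated contrast toward no effect. In a safety table that error gives false reassurance. Protocol 9.5.2.2 says the impact of ADA on safety endpoints will be evaluated when relevant, so these tables will be read for that purpose.

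**Working it through.** The documents give no figure for this table, so there is nothing to reproduce. The check has a schedule count, which rests on the documents, and an illustration, which rests on assumed rates.

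**Inputs.** From Protocol 1.3, row "Study drug administration": visits 2, 4, 5, 6, 8 and 9, nominally Days 1, 8, 15, 22, 29 and 36. Row "Blood sampling for ADA": post-Baseline visits 5, 7, 10, 12 and 14, nominally Days 15, 24, 43, 71 and 99. SAP 10.2.1 ends the TEAE window 56 days after the final dose, nominally 36 + 56 = Day 92. The Day 15 ADA sample is taken as predose; Protocol 8.7 says this for immunological assessments, though under the pharmacodynamics heading.

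**Schedule count.**

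| First positive sample | Infusions before | Infusions after | Share of Days 1–92 before the sample |
|---|---|---|---|
| Day 15 | 2 | 4 | 14/92 = 15% |
| Day 24 | 4 | 2 | 23/92 = 25% |
| Day 43 | 6 | 0 | 42/92 = 46% |
| Day 71 | 6 | 0 | 70/92 = 76% |
| Day 99 | 6 | 0 | 100% |

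For three of the five possible first-positive visits, every infusion precedes detection. A first positive on Day 99 comes after the nominal TEAE window has closed.

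**Illustration for infusion-linked reactions in category 3.** Assume six infusions, antibody onset at first detection, and a per-infusion risk multiplied by RR after onset. The apparent ratio against never-positive participants is (infusions before × 1 + infusions after × RR) / 6. With RR = 3:
- All first positive on Day 15: (2 + 4 × 3)/6 = 2.33.
- All on Day 24: (4 + 2 × 3)/6 = 1.67.
- All on Day 43 or later: 6/6 = 1.0.
- Equal spread over the five samples: mean infusions after = (4 + 2 + 0 + 0 + 0)/5 = 1.2, so (4.8 + 1.2 × 3)/6 = 1.4.

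Counting participants with at least one reaction gives nearly the same. Incidence is 1 − (1 − p)^before × (1 − RR × p)^after, divided by 1 − (1 − p)^6. For assumed p from 0.5% to 2% and RR = 3, the ratios are 2.30 to 2.19 (Day 15), 1.66 to 1.62 (Day 24), 1.39 to 1.36 (equal spread) and 1.0 (Day 43 or later). With RR = 1 the ratio is 1.0 throughout.

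If the Day 15 sample were postdose, the Day 15 counts would be 3 before and 3 after. The equal-spread mean after is then (3 + 2)/5 = 1.0, and the ratio (5 + 1 × 3)/6 = 1.33.

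**If onset precedes detection by one sample.** Infusions before true onset are then 1, 2, 4, 6 and 6 for the five first-positive visits, a total of 19, against 2 + 4 + 6 + 6 + 6 = 24 before detection. So 24 − 19 = 5 of the 24 pre-detection infusions were given with antibody present. With RR = 3, the pre-detection infusions carry an average ratio of (19 + 5 × 3)/24 = 1.42. A split at detection would place some genuinely ADA-related reactions in the before group.

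**The case against.** The strongest defence is that the plan already serves the purpose. Day 99 roughly matches the TEAE period. Reactions may be few, and the all-region listing supports case-by-case review of timing, which may say more than sparse cells. Five post-Baseline samples locate onset poorly, and SAP 9.3.1 calls an otherwise negative sample inconclusive when drug concentration exceeds the assay's tolerance limit, so detection can lag onset. A split at detection would misplace some events, and its after group may be nearly empty. The outputs are descriptive, and the formal ADA objective names PK and PD only.

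Much of this stands, and it limits what can be claimed. A reader might infer that events before a first positive sample cannot be due to ADA, or that dilution is certain. The documents do not support either, as the lag calculation shows. A reader might also think the Day 43 window used for MG-ADL avoids the problem; it does not, because an early score is still grouped by later status.

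What does not stand is that the listing replaces a table. It gives no incidence, no denominator and no exposure at risk, and the before/after table exists for Japan only.

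**Conclusion.** The point holds for category 3 participants. In the all-region tables their events before first detected positivity are counted as events in treatment-emergent positive participants, and for infusion-linked reactions the schedule leaves no later infusion for anyone first positive from Day 43 on. The likely effect is attenuation: a threefold per-infusion risk appears as about 1.4-fold under equal spread, from 1.0 (all Day 43 or later) to 2.3 (all Day 15). This assumes onset close to detection, six infusions and rates the documents do not give. With no true effect, no false signal arises in this model.

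Three wider readings are not supported:
- That all reactions under ADA positivity preceded any detected antibody. Category 4 was positive at Baseline, and the point does not touch category 8.
- That the 1.4-fold figure describes the all-TEAE tables. It counts infusions, so it fits infusion reactions and the anaphylactic reactions that SAP 13.8 ties to a dosing day or the day after. Hypersensitivity is selected by a standard query without that tie, and participants first positive at Day 43 or 71 still have TEAE time after detection.
- That the Japan and all-region tables would conflict on the same events. They differ in population, and 11.1 covers immune-related TEAEs.

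No efficacy conclusion or error rate is affected. The change should be made, but it is not critical.

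**What to change.** Keep the ever-positive category tables in SAP 9.3.2. For the reaction table and the TEAE incidence table, add the split already defined in SAP 11.1 for all participants: before treatment-emergent ADA positivity, after it, and never treatment-emergent positive. In the added tables:
- Label the split as relative to first detected treatment-emergent positivity.
- Show exposure at risk in each group, as infusions for reactions and participant-weeks for TEAEs, because one participant can contribute both before and after.
- Show the Baseline-positive categories (4, 5 and 6) separately.
- Add a footnote that, with sparse sampling, an event shortly before a first positive sample may still be ADA-related.

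The cost is a short SAP amendment and extending a table already to be programmed for Japan. First positivity by visit is already derived for all regions. The downside is small cells in the after group.

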9.4 Immunology

All analyses described in this section will be based on the SS.

9.4.1 Serum complement levels and plasma complement levels

Serum (C3 and C4) and plasma (C3a and C5a) complement variables will be listed by treatment group and RLZ total, visit and time point including changes from Baseline. Descriptive summaries will be presented for both absolute values and changes from Baseline for all study participants, and separately for study participants who experience an infusion reaction or hypersensitivity reaction or anaphylactic reaction. The selection criteria of infusion reaction or hypersensitivity reaction are described in [Section 13.8](#).

Measurements BLQ will be imputed with half of the LLOQ for the purpose of calculating change from Baseline. Measurements above the limit of quantification (ALQ), if applicable, will be imputed to the upper limit of quantification.

Serum (C3 and C4) and plasma (C3a and C5a) complements results will be listed.

9.4.2 Serum cytokines

Serum cytokines will be summarized by treatment group and RLZ total, visit and time point for both absolute values and changes from Baseline, for all study participants, and separately for study participants experiencing with serious or severe headache and/or infusion reactions or hypersensitivity reaction. The selection criteria of those events are described in [Section 13.8](#).

Measurements BLQ will be imputed with half of the LLOQ for the purpose of calculating change from Baseline. Measurements ALQ, if applicable, will be imputed to the upper limit of quantification.

Cytokines results will be listed.

